6.2.4.4. Cardiac Function Monitoring

Subjects will undergo a thorough monitoring for cardiac/vascular AEs and protective measures are in place to exclude subjects at risk from trial participation.

At baseline, subjects undergo an ECG, an echocardiography (or MUGA if ECHO cannot be performed) and testing for N-terminal pro b-type Natriuretic Peptid levels (NT-proBNP, heart-failure screening). Testing for NT-proBNP will be repeated every 2 weeks (3 weeks for the cutaneous squamous-cell carcinoma cohort) for 3 months and thereafter monthly (every second cycle for the cutaneous squamous-cell carcinoma cohort) or in case of any suspicion regarding cardiac/vascular damage of any type (then combined with ECG and echocardiography, again).

A single, 12-lead ECG will be performed at time points outlined in [Section 6.1.12](#).

All ECG monitoring is to be performed locally at the Investigator site.

The subject should be relaxed and in a recumbent or semi-recumbent position at least 5 minutes before recording an ECG.

Additional ECG testing may be performed at the Investigator's discretion if deemed clinically warranted.

6.2.4.5. Clinical Laboratory Assessment

Samples for laboratory testing listed as below will be collected at time points according to the SoAs in [Table 5](#), [Table 6](#) and [Table 7](#). All tests are performed locally.

- Hematology/coagulation, clinical chemistry results must be available and reviewed and deemed acceptable by the Investigator or authorized designee, prior to CTL-002/PD-1/PD-L1 administration
- Clinically significant abnormal tests must be repeated to confirm the nature and degree of the abnormality. When necessary, appropriate ancillary investigations should be initiated. If the abnormality fails to resolve or cannot be explained by events or conditions unrelated to the study medication or its administration, the Medical Monitor must be consulted
- The clinical significance of an abnormal test value, within the context of the disease under study, must be determined by the Investigator which includes significant shifts from baseline within the range of normal that the Investigator considers to be clinically important

Table 8 Safety Laboratory Testing

Hematology	Hemoglobin, hematocrit, RBC, WBC with differential, ANC, AMC, platelet count
Clinical Chemistry	CRP, creatinine, LDH, calcium, electrolytes (sodium and potassium), total bilirubin, GGT, albumin, alkaline phosphatase, AST, ALT, lipase or amylase and glucose
Coagulation	
 • Includes: αPTT, PT/INR • INR/PT should be measured daily for any subject experiencing ALT or AST elevations ≥ 3 x ULN with concomitant elevation in bilirubin ≥ 2 x ULN until resolution to baseline of the liver function test abnormality. • AT III • D-Dimer
Serology	Analysis for HIV1 and HIV2, HBV, HCV, TB, SARS-CoV-2
Urinalysis	pH, ketones, specific gravity, bilirubin, protein, blood and glucose will be assessed by dipstick.

Abbreviations: α PTT = activated partial prothrombin time; AMC = absolute monocyte count; ALT = alanine aminotransferase; ANC = absolute neutrophil count; AST = aspartate aminotransferase; AT III = Antithrombin III; CRP = C-reactive protein; GGT = gamma-glutamyltransferase; HBV = hepatitis B virus; HCV = hepatitis C virus; HIV1 = human immunodeficiency virus 1; HIV2 = human immunodeficiency virus 2; INR = international normalized ratio; LDH = lactate dehydrogenase; PT = prothrombin time; RBC = red blood cell count; TB = tuberculosis; ULN = upper limit of normal; WBC = white blood cell count

6.2.4.6. Pregnancy Testing

Serum β -human chorionic gonadotropin (β -HCG) pregnancy test will be performed at Screening for all women of childbearing potential. A urine pregnancy test must be repeated prior to each dose of CTL-002/the defined checkpoint inhibitor and then at the End of Treatment Visit and at the Safety Follow-up Visit (refer to the SoAs in [Table 5](#), [Table 6](#) and [Table 7](#)). Any positive urine test must be confirmed with a serum pregnancy test.

Additional urine pregnancy tests may be done during the course of the study at the Investigator's discretion if deemed clinically warranted, with a urine dipstick test, to be performed locally.

Pregnancy must be reported from the time of the signing of the ICF until 5 months after last study treatment.

6.2.4.7. Pharmacokinetics

The PK of CTL-002 given as monotherapy and/or in combination with the defined checkpoint inhibitor will be measured from blood samples collected at the start of treatment and at various subsequent time points (Part A, Phase 1). Additional PK data may be evaluated in the expansion cohorts (Part B, Phase 2 a).

Blood samples will be taken at the start of treatment and at various subsequent time points to determine, if antibodies directed against CTL-002 may have developed.

6.2.4.8. Pharmacodynamics and Monitoring of Systemic Cytokines/Chemokines

The pharmacodynamics of CTL-002 administered as monotherapy and/or in combination with the defined checkpoint inhibitor will be determined from peripheral blood, urine and tumor biopsies as available. Urine GDF-15, serum total GDF-15, intratumoral GDF-15 and tumor immune cell infiltration will be determined.

Serum samples will be collected as defined in the SoAs in [Table 5](#), [Table 6](#) and [Table 7](#) for measurement of cytokines, chemokines and other circulating biomarkers to assess pharmacodynamic effects as well as safety. [Table 9](#) below provides a summary of pharmacodynamic laboratory assessments for this study.

Table 9 Pharmacodynamic Laboratory Assessments

Assessment	Analysis	Sample
GDF-15	GDF-15	Serum
Cytokines and chemokines	May include but are not limited to: TNF- α , IFN- γ , IL-1 β , IL-2, IL-4, IL-6, IL-8, IL-10, IL-12p70, IL-13, CXCL9 (MIG) and CXCL10 (IP-10)	Serum
Molecular/transcriptional profiling	May include but are not limited to: TMB, TCR	Blood

Abbreviations: IFN = interferon; IL = interleukin; IP = interferon-gamma induced protein 10 kD, CXCL10; MIG = monokine induced by gamma; TNF- α = tumor necrosis factor alpha.

6.2.4.9. Exploratory Assessments

Various molecular and immunohistochemical biomarkers and immune parameters (e.g., including but not limited to molecular profiling, mutation status, mutational burden or other markers of interest relating to immune activation or disease may be explored) will be assessed in peripheral blood, serum, urine and tumor tissue.

The Sponsor might conduct future retrospective serum biomarker testing on specimens (retention aliquots) specifically collected for future biomedical research during this clinical trial to identify serum factors (e.g., but not limited to metabolites, soluble growth factors, cytokines, chemokines,) important for anti-GDF-15 (CTL-002) therapy. This biomarker testing to address emergent questions will not be described elsewhere in the protocol (as part of the main trial) and will only be conducted on specimens from appropriately consented subjects. Retrospective biomarker studies will be conducted with appropriate biostatistical design and analysis and compared to PK/Pharmacodynamic results, previously assessed biomarkers or clinical outcomes.

6.2.5. Efficacy Assessment

6.2.5.1. Tumor Assessments (CT/MRI/PET-Scan, local Testing)

Tumor response is evaluated according to institutional standards using RECIST V1.1 as well as iRECIST criteria (refer to [Appendix 2](#)). For the purposes of this study, subjects will undergo evaluation at Screening for a baseline scan and should be re-evaluated every 8 weeks (6-9 weeks for the cutaneous squamous-cell carcinoma cohort only) and/or from the End of Treatment Visit, then after this time response assessments may be performed as per local institutional guidelines until the end of the Efficacy and Survival Follow-up. Refer to the SoAs in [Table 5](#), [Table 6](#) and [Table 7](#).

All lesions identified at Screening/baseline will be consistently followed using the unique lesion number assigned at Screening/baseline and need to be documented in the subject file and in the eCRF. Lesions that are being biopsied should not be included in the RECIST assessment.

The same method of assessment (imaging modality, e.g., MRI, CT) must be used to characterize each identified and reported lesion at baseline and during all follow-up examinations for an individual subject. If there is a change in modality, then the trial site may be asked to explain the reason for the change in the eCRF. A change in modality may be considered a protocol deviation.

Each efficacy time point/visit may be completed up to a window of ± 7 days in the Core Study Period and a window of ± 2 weeks in the Efficacy and Survival Follow-up period.

A central reading of the images by a reading center will be performed post-hoc in addition to local reading by the Investigator during the trial.

Definition of Progressive Disease according to RECIST V1.1 and iRECIST:

RECIST assessments will be used to identify subjects with possible progression of disease (Eisenhauer et al, 2009). As defined by modified RECIST V1.1 criteria for immune-based therapeutics or iRECIST criteria (Seymour et al., 2017), the date of initial potential progression by RECIST scanning will be defined as the immune unconfirmed progressive disease (iUPD) date. Subjects with an iUPD date who are stable will continue to participate in the study as planned and be reassessed for progression 4 to 8 weeks after the initial assessment. If the confirmatory assessment supports PD, the date of disease progression will be the iUPD date. If the confirmatory assessment does not support PD, the subject does not have disease progression and the iUPD date is ignored; such subjects will remain in the study as planned and continue the next imaging evaluation as planned per protocol.

Anti-tumor activity will be assessed per Investigator assessment using RECIST V1.1 and the Immune Response Criteria according to iRECIST (see details in [Appendix 2](#)), as described below.

- Contrast CT scans of the chest, abdomen and pelvis, MRI or positron emission tomography-computed tomography (PET-CT)
- Disease response and disease progression will be evaluated in this study using RECIST and iRECIST criteria
- Subjects with brain and/or leptomeningeal metastases that are symptomatic or untreated or that require current therapy will not be eligible for the study. Brain imaging must not be older than 12 weeks. Results with abnormal/unexpected findings of brain MRI should be discussed with the Medical Monitor as part of the screening process
- The same method of assessment and the same technique should be used to characterize each identified and reported lesion at baseline and during follow-up. If there is a change in modality, then the trial site may be asked to explain the reason for the change in the eCRF. A change in modality may be considered a protocol deviation

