1.10. Trial Endpoints

1.10.1. Primary Endpoints

Part A (Phase 1; dose escalation):

- Evaluation of the number of subjects with AEs, including serious adverse events (SAEs), clinical laboratory data, vital signs, electrocardiograms (ECGs), physical examination (including neurological assessment) and Eastern Cooperative Oncology Group (ECOG) performance status

Determination of DLTs and maximum tolerated dose (MTD) in Part A of the study using the National Cancer Institute Common Terminology Criteria for Adverse Events (NCI-CTCAE) Version 5.0

Part B (Phase 2a; expansion):

- Evaluation of the clinical efficacy according to Response Evaluation Criteria in Solid Tumors (RECIST) V1.1 of CTL-002 in combination with an anti-PD-1 checkpoint inhibitor by assessment of:
 - The proportion of subjects with tumor shrinkage, a confirmed partial response (PR) and/or complete response (CR), and overall response rate (ORR)
 - The interval between the date of first CTL-002 administration and first documented evidence of a PR or CR (time to response [TTR])
 - The interval between the date of first documented evidence of PR or CR, until first documented evidence of disease progression or death, due to any cause (duration of response [DOR])
 - The interval between the date of first CTL-002 administration and the earliest date of disease progression or death (progression free survival [PFS])
 - The interval between the date of first CTL-002 administration and date of death due to any cause (overall survival [OS])
- Evaluation of the number of subjects with AEs, including SAEs, clinical laboratory data, vital signs, ECGs, physical examination (including neurological assessment), and ECOG performance status

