1.10.3. Exploratory Endpoints**Part A (Phase 1; dose escalation):**

- Evaluation of GDF-15 serum levels and their correlation with pharmacodynamic and clinical response
- Immune cell phenotyping including activation status and immune cell infiltration pattern in tumor tissue
- Molecular profiling (e.g., transcriptional profiling, mutational status, mutational burden of tumor tissue)
- To assess anti-tumor efficacy (PR, CR, DOR, PFS, and OS) of CTL-002 in combination with an anti-PD-1 checkpoint inhibitor using iRECIST ([Seymour et al., 2017](#)), criteria in solid tumors in subjects with advanced-stage solid tumors that relapsed post or were refractory to a prior anti-PD-1/PD-L1 therapy

Part B (Phase 2a; expansion):

- In subjects that undergo tumor biopsy: Immune cell phenotyping including activation status and immune cell infiltration pattern in tumor tissue
- In subjects that undergo tumor biopsy: Molecular profiling (e.g., transcriptional profiling, sequencing of genes of interest, mutational status, mutational burden of tumor tissue) and evaluation of GDF-15 levels
- To assess anti-tumor efficacy (PR, CR, DOR, PFS, and OS) of CTL-002 in combination with an anti-PD-1 checkpoint inhibitor using iRECIST criteria ([Seymour et al., 2017](#)), in solid tumors that relapsed on or were primary refractory to a prior anti-PD-1/PD-L1 therapy
- To assess in subjects with advanced-stage cutaneous squamous-cell carcinoma that relapsed on or were primary refractory to a prior anti-PD-1/PD-L1 therapy: the anti-tumor efficacy (PR, CR, DOR, PFS, and OS) of CTL-002 in combination with cemiplimab checkpoint inhibitor using WHO bidimensional measurements
- The proportion of subjects with tumor shrinkage, a confirmed partial PR and/or CR, and ORR after receiving stereotactic radiotherapy according to RECIST V1.1 (ORR-2)
- The interval between application of stereotactic radiotherapy and first documented evidence of a PR or CR according to RECIST V1.1 (TTR-2)
- The interval between the date of first documented evidence of PR or CR after having received stereotactic radiotherapy, until first documented evidence of disease progression or death, due to any cause according to RECIST V1.1 (DOR-2)

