4.6. Treatment Beyond Progression

The drugs used in this study are meant to induce an immune response against the subject's tumor and may not have an immediate effect on the tumor. In addition, the expected mechanism of action involves an infiltration of T-cells and inflammatory cells and local release of inflammatory cytokines. Therefore, it is expected that initial radiographic progression may not be indicative of subsequent lack of response. Treatment may continue in spite of early radiographic progression,

including appearance of new lesions, in the absence of symptomatic progression as long as the subject has not had an AE that meets the criteria for treatment discontinuation.

Treatment past initial RECIST-defined radiographic progression may continue according to Investigator judgment, in consultation with the Medical Monitor, based on the subject's overall clinical status, overall tumor burden, and rate of progression, taking into account the subject's other treatment options and need for urgent intervention (decisions regarding subject treatment should be made according to site standard of care as determined by the Investigator).

For example, a subject may continue treatment if a tumor assessment shows improvement or stable disease compared to the previous scan, even if there is progression compared to the baseline scan. Investigators may schedule an additional tumor assessment within 8 weeks after a scan showing progression, in order to reassess the subject's response. Subjects may be treated after progression if they meet these criteria:

- Investigator-assessed potential clinical benefit
- No disease-related clinical deterioration
- Absence of progressive tumor at critical anatomical sites (e.g., cord compression) requiring urgent alternative medical intervention
- Subject has not had an AE that meets the criteria for treatment discontinuation

If treatment is continued in spite of radiographic progression, the Investigator should record the rationale, and the subject must be informed that treatment beyond initial progression is not standard of care, and the Investigator should discuss potential risks and alternative treatment options.

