where known residual benign tumors can remain). When effusions are known to be a potential adverse effect of treatment (e.g., with certain taxane compounds or angiogenesis inhibitors), the cytological confirmation of the neoplastic origin of any effusion that appears or worsens during treatment when the measurable tumor has met criteria for response or SD is advised to differentiate between response or SD and PD.

A 1.3 Tumor Response Evaluation

All subjects will have their BEST RESPONSE from the start of study treatment until the end of treatment classified as outlined below. Refer to [Table 11](#) and [Table 12](#).

Complete Response (CR) – disappearance of all *target* and *non-target* lesions and normalization of tumor markers. Pathological lymph nodes must have short axis measures <10 mm (*Note: continue to record the measurement even if <10 mm and considered CR*). Tumor markers must have normalized. Residual lesions (other than nodes <10 mm) thought to be non-malignant should be further investigated (by cytology or PET scans) before CR can be accepted.

Partial Response (PR) – at least a 30% decrease in the sum of measures (longest diameter for tumor lesions and short axis measure for nodes) of target lesions, taking as reference the baseline sum of diameters. Non-target lesions must be non-PD.

Stable Disease (SD) – neither sufficient shrinkage to qualify for PR nor sufficient increase to qualify for PD taking as reference the smallest sum of diameters on study.

Progressive Disease (PD) – at least a 20% increase in the sum of diameters of measured lesions taking as references the smallest sum of diameters recorded on study (including baseline) AND an absolute increase of ≥ 5 mm. Appearance of new lesions will also constitute PD (including lesions in previously unassessed areas). In exceptional circumstances, unequivocal progression of non-target disease may be accepted as evidence of disease progression, where the overall tumor burden has increased sufficiently to merit discontinuation of treatment, for example where the tumor burden appears to have increased by at least 73% in volume (which is the increase in volume when all dimensions of a single lesion increase by 20%). Modest increases in the size of one or more non-target lesions are NOT considered unequivocal progression. If the evidence of PD is equivocal (target or non-target), treatment may continue until the next assessment, but on further documentation, the earlier date must be used.

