Table 11 Integration of Target, Non-Target, and New Lesions Response Assessment (Appendix 1)

Target Lesions	Non-Target Lesions	New Lesions	Overall Response	Best Response for this Category Also Requires
Subjects with target lesions ± non-target lesions				
CR	CR	No	CR	Normalization of tumor markers All tumor nodes <10 mm
CR	Non-CR/Non-PD	No	PR	
CR	Not all evaluated	No	PR	
PR	Non-PD/not all evaluated	No	PR	
SD	Non-PD/not all evaluated	No	SD	
Not all evaluated	Non-PD	No	NE	
PD	Any	Any	PD	
Any	PD	Any	PD	
Any	Any	Yes	PD	

Abbreviations: CR = complete response; NE = Not Evaluable; PD = progressive disease; PR = partial response; SD = stable disease.

Note: Subjects with a global deterioration of health status requiring discontinuation of treatment without objective evidence of disease progression (or evidence of unequivocal disease progression) at that time should be reported as “symptomatic deterioration”. This is a reason for stopping therapy, but is NOT objective PD. Every effort should be made to document the objective progression even after discontinuation of treatment.

The BOR can be interpreted from [Table 12](#).

Table 12 Response Assessment After Subsequent Scan (Appendix 1)

Response: First Time Point	Subsequent Time Point	BEST Overall Response	Also Requires
CR	CR	CR	Normalization of tumor markers. All tumor nodes <10 mm.
CR	PR	SD, PD or PR (see comment*)	
CR	SD	SD provided minimum criteria for SD duration met, otherwise, PD	
CR	PD	SD provided minimum criteria for SD duration met, otherwise, PD	
CR	NE	SD provided minimum criteria for SD duration met, otherwise NE	
PR	CR	PR	
PR	PR	PR	
PR	SD	SD	
PR	PD	SD provided minimum criteria for SD duration met, otherwise, PD	
PR	NE	SD provided minimum criteria for SD duration met, otherwise NE	
NE	NE	NE	

Abbreviations: CR = complete response; NE = Not Evaluable; PD = progressive disease; PR = partial response; SD = stable disease.

* may consider PR providing initial “CR” likely PR on subsequent review – then original CR should be corrected. Recurrence of lesion after true CR is PD.

A 1.4 Frequency of Tumor Re-Evaluation

Tumors should be assessed at baseline, Week 8 and then every 8 weeks. Additional assessments may be performed thereafter according to local institutional guidelines.

A 1.5 Date of Progression

This is defined as the first day when the RECIST (Version 1.1) criteria for PD are met.

A 1.6 Reporting of Tumor Response

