APPENDIX 2. IMMUNE RESPONSE EVALUATION CRITERIA IN SOLID TUMORS (iRECIST)

As defined by modified RECIST V1.1 criteria for immune-based therapeutics or iRECIST criteria ([Seymour et al., 2017](#)), the date of initial potential progression by RECIST scanning will be defined as the iUPD date. Subjects with an iUPD date who are stable will continue to participate in the study as planned and be reassessed for progression 4 to 8 weeks after the initial assessment. If the confirmatory assessment supports PD, the date of disease progression will be the iUPD date. If the confirmatory assessment does not support PD, the subject does not have disease progression and the iUPD date is ignored; such subjects will remain in the study as planned and continue the next imaging evaluation as planned per protocol.

Table 13 Comparison of RECIST V1.1 and iRECIST (Appendix 2)

	RECIST V1.1	iRECIST
Definitions of measurable and nonmeasurable disease; numbers and site of target disease	Measurable lesions are ≥ 10 mm in diameter (≥ 15 mm for nodal lesions) maximum of 5 lesions (2 per organ); all other disease is considered non-target (must be ≥ 10 mm in short axis for nodal disease)	No change from RECIST V1.1; however, new lesions are assessed as per RECIST V1.1 but are recorded separately on the eCRF (but not included in the sum of lesions for target lesions identified at baseline)
CR, PR, or SD	Cannot have met criteria for progression before CR, PR, or SD	Can have had iUPD (one or more instances), but not iCPD, before iCR, iPR, or iSD
Confirmation of CR or PR	Only required for non-randomized trials	As per RECIST V1.1
Confirmation of SD	Not required	As per RECIST V1.1
New lesions	Result in progression; recorded but not measured	Results in iUPD but iCPD is only assigned on the basis of this category if at next assessment additional new lesions appear or an increase in size of new lesions is seen (≥ 5 mm for sum of new lesion target or any increase in new lesion non-target); the appearance of new lesions when none have previously been recorded, can also confirm iCPD
Independent blinded review and central collection of scans	Recommended in some circumstances – e.g., in some trials with progression-based endpoints planned for marketing approval	Collection of scans (but not independent review) recommended for all trials
Confirmation of progression	Not required (unless equivocal)	Required

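### Section 6.2.5.1 puts the iRECIST rule that discards an unconfirmed progression under a heading that also covers RECIST V1.1, and A 1.3 leaves best response open past progression; both conflict with the RECIST V1.1 rules behind the primary endpoints

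*Protocol*

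**What the plan says.** Section 1.10.1 sets the Part B primary efficacy endpoints as "Evaluation of the clinical efficacy according to Response Evaluation Criteria in Solid Tumors (RECIST) V1.1". They include ORR, TTR, DOR and PFS. Section 1.10.3 lists as exploratory: "To assess anti-tumor efficacy (PR, CR, DOR, PFS, and OS) of CTL-002 in combination with an anti-PD-1 checkpoint inhibitor using iRECIST criteria".

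Progression is then defined in more than one place.

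- **Section 6.2.5.1** carries the heading "Definition of Progressive Disease according to RECIST V1.1 and iRECIST". The text below it uses RECIST to flag possible progression, labels that date iUPD (the iRECIST term for unconfirmed progression), and has stable subjects reassessed 4 to 8 weeks later. It continues: "If the confirmatory assessment does not support PD, the subject does not have disease progression and the iUPD date is ignored". No separate rule for RECIST V1.1 follows.
- **Appendix 1, A 1.5**, on the date of progression: "This is defined as the first day when the RECIST (Version 1.1) criteria for PD are met".
- **Table 10** (section 8.3.3), titled for RECIST V1.1, ends PFS and DOR at the first progression or death. It does not itself define progression.
- **Table 13** (Appendix 2), RECIST V1.1 column, requires no confirmation of progression unless it is equivocal. On CR, PR or SD it says: "Cannot have met criteria for progression before CR, PR, or SD".

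On the response window, A 1.3 states: "All subjects will have their BEST RESPONSE from the start of study treatment until the end of treatment classified as outlined below". Section 4.6 allows dosing to go on after progression: "Treatment past initial RECIST-defined radiographic progression may continue according to Investigator judgment".

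**The concern.** Two readers can follow the protocol faithfully and obtain different primary results. One takes 6.2.5.1 at its heading and treats an unconfirmed RECIST V1.1 progression as if it had not happened. The other follows A 1.5 and Table 13 and counts it. In the same way, a reader of A 1.3 alone keeps looking for a best response until treatment stops, whereas a reader of Table 13 stops at progression. Because section 4.6 permits treatment after progression, the interval between the two stopping points can be real.

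Both looser readings err in the direction that favours the drug. PFS and DOR lengthen, and the ORR and the first-stage responder count can rise. The RECIST V1.1 and iRECIST analyses, which the protocol means to keep apart, would also begin to merge.

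This is more than a programming detail. Under 6.2.5.1, investigators assess response during the trial and central reading is only post hoc, so sites apply whichever rule they take from the protocol.

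**Working it through.** **Design figures.** No figure in the protocol tests this point directly. The two-stage rules that use the responder count reproduce. Power is the sum over first-stage counts x at or above the continuation threshold of P(X1 = x) × P(X2 ≥ r − x), with exact binomials, where r is the final responder threshold:

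| Cohorts | Rule | True rate | Stated power | Computed |
|---|---|---|---|---|
| Bladder, HCC, NSCLC, melanoma | ≥1/14, then ≥4/27 | 20% | 80% | 80.7% |
| CSCC | ≥2/12, then ≥6/36 | 25% | 80% | 80.3% |
| Colorectal | ≥1/10, then ≥4/29 | 20% | 80% | 80.1% |

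The design arithmetic is not in question. What matters here is which subjects count as responders and when progression is dated.

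**Progression date.**

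| Question | 6.2.5.1, as headed | A 1.5, Table 10, Table 13 (RECIST V1.1) |
|---|---|---|
| Is confirmation needed? | Yes, at 4 to 8 weeks | No, unless equivocal |
| First PD not supported at rescan | Date discarded | Remains the event |
| First PD supported at rescan | Dated at first PD | Dated at first PD |

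The rules agree when progression is confirmed and disagree when it is not. A 1.3 has its own provision for equivocal progression: treatment may go on, and if progression is then documented the earlier date applies. That is not a general discarding of unconfirmed dates.

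**Effect on one subject's PFS (8-weekly scans, nivolumab cohorts).**

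- Progression on the week-8 scan gives an event at week 8 under A 1.5.
- Under 6.2.5.1 the rescan falls at week 8 + 4 = 12 to 8 + 8 = 16.
- If that rescan does not support progression, the next scheduled scan is week 16 (after a week-12 rescan) or week 24 (after a week-16 rescan).
- A scan-based event therefore moves from week 8 to week 16 at the earliest, or week 24: a shift of at least 16 − 8 = 8 or 24 − 8 = 16 weeks, unless the subject dies first.
- DOR shifts in the same way when the discarded progression follows a response.

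**Effect on the response count.** A 1.3 states no cut at progression, and Table 12, which it points to for best overall response, has no row beginning with progression. The one explicit bar on a later RECIST V1.1 response is a single cell of Table 13, in the iRECIST appendix. In a 14-subject cohort the continuation threshold is one responder, so counting or not counting one such subject separates 0/14 from 1/14.

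**The case against.** The strongest answer is that the two dates belong to two criteria sets. The discarding rule in 6.2.5.1 is introduced as the iRECIST definition, uses an iRECIST category, and is repeated in Appendix 2. Sections 1.10.1 and 1.10.3 assign RECIST V1.1 to the primary endpoints and iRECIST to the exploratory ones. Table 10, A 1.5 and Table 13 are consistent for RECIST V1.1. Section 4.6 governs treatment and still calls the event progression; it erases nothing. The study is explorative, and detailed derivations are commonly left to the SAP, which was not available here.

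Much of this stands: the intended reading can be recovered. But 6.2.5.1 names RECIST V1.1 in its heading, offers no other rule for it, and does not restrict the discarding to exploratory endpoints. Sections 3.3 and 3.5 also speak of confirmed progression, which makes the looser reading natural at a site. An SAP does not remove a contradiction that investigators apply while assessing patients.

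A reader might go further and infer that the protocol counts post-progression responses in the primary ORR. It does not: no passage says so, and Table 13 says the opposite.

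A reader might also want an inflation figure. If 2% to 10% of subjects responded after progression (an assumption), the chance of at least one among 14 would be 1 − 0.98^14 = 25% to 1 − 0.90^14 = 77%. That is not the chance of a changed decision, which also needs zero conventional responders. Taking the two kinds of response as mutually exclusive:

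- at a 10% conventional rate (assumed), 0.90^14 − 0.88^14 = 6% to 0.90^14 − 0.80^14 = 19%;
- at a 5% conventional rate (assumed), 0.95^14 − 0.93^14 = 13% to 0.95^14 − 0.85^14 = 39%.

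Even these presume every such response is miscounted. Expansion also needs Safety Review Committee and sponsor agreement, and the final rule still needs 4/27. Section 1.8.5 describes one Part A subject with a deep partial response after progression and radiotherapy. That shows such a course can occur but gives no rate.

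**Conclusion.** The point holds as an internal contradiction about the primary endpoints.

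- **PFS and DOR.** As headed, 6.2.5.1 conflicts with A 1.5 and Table 13. Applied literally, it lengthens PFS and DOR for each subject whose first progression is not confirmed, by the 8 to 16 weeks shown above for a week-8 progression under 8-weekly imaging and barring death.
- **ORR and first-stage count.** This part is weaker. The A 1.3 window conflicts with Table 13, and a post-progression response enters only if A 1.3 is read without Table 13, or if the progression has first been discarded under 6.2.5.1.

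The overall size is unknown. The documents give no rate of unconfirmed progression or of response after progression, so none of the percentages under the objection is a finding. Stated sample sizes and power are unaffected.

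**What to change.** Three wording changes:

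1. In 6.2.5.1, limit the iUPD and confirmation paragraph to the exploratory iRECIST endpoints.
2. In the same section, state that for primary PFS and DOR the event is the first RECIST V1.1 progression as dated in A 1.5, even if treatment continues or later scans improve.
3. In A 1.3, close the RECIST V1.1 best-response window at first RECIST V1.1 progression, in line with Table 13. Report later responses only under iRECIST, outside the ORR and the two-stage responder counts.

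The changes concern analysis definitions only. They leave the treatment-beyond-progression rules in section 4.6 untouched and need no new visits, data or subjects. The cost is that PFS, DOR and ORR may look slightly less favourable.
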